### Consultant

Name: [name]  
Affiliations: Founder and CEO, Noctem, LLC  
Professor of Psychiatry (on leave), University of Pittsburgh School of Medicine  
Facility: VA Pittsburgh Healthcare System, Pittsburgh, PA, USA  
Contact: [contact], [[contact]](mailto:[contact])

There are 5 VAMCs/Healthcare Systems involved in this study. Pittsburgh is the coordinating/hub site. The participating sites are Baltimore, Durham, Minneapolis, and Philadelphia. This is a stepped-wedge trial. Training in BBTI will occur at approximately the same time for all sites, the third month of the study. However, sites' access to implementation strategies and support will be staggered (see Figure 2).

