## 5.1 Study Procedures

### 5.1 Study Design

Overview of Experimental Design and Timeline. This is a four-year, stepped-wedge, hybrid III implementation-effectiveness trial comparing two conditions: training PCMH clinicians to deliver BBTI (BBTI) vs. training clinicians to deliver BBTI augmented by access to, and support for, a bundle of expert-consensus implementation strategies (BBTI+IS). The goal of this trial is to determine if a bundle of implementation strategies can improve the uptake and sustainable delivery, and treatment outcomes, of BBTI in VA PCMH settings. Three approaches will be used to measure outcomes: (1) RE-AIM framework; (2) CFIR-guided qualitative interviews, with site PIs and PCMH clinicians, to identify barriers and facilitators related to implementation outcomes; and (3) surveys, completed by site PIs and PCMH clinicians, to identify utilization of specific implementation strategies. Four sites were invited to participate (Baltimore, Durham, Minneapolis, and Philadelphia) with Pittsburgh serving as the coordinating site, responsible for: (1) oversight of all study activities, (2) development and conduct of BBTI training, (3) providing support for the implementation strategies, and (4) directing data collection and analysis efforts.

As depicted in Figure 2, after study start-up procedures, the first step will involve training PCMH clinicians in BBTI at all sites. After BBTI training, site 1 (randomly selected) will have immediate access to, and support for, the bundle of implementation strategies for 12-months; this is the implementation phase of the trial. Sites 2, 3, and 4 will enter the pre-implementation monitoring phase for 6-, 12-, and 18-months, respectively, followed by their own 12-month implementation phase (random order). After each site has completed their 12-month implementation phase, access to the implementation strategies will be removed and each site will begin a 6-month post-implementation monitoring phase; however, for sites 1-3 we will continue to collect data to evaluate long-term sustainability through study month 39. Data collection will occur through all phases of the trial.

Figure 1. Study timeline.

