similar phases and across sites for similar phase comparisons. It will also allow for within site comparisons to evaluate the impact from pre- to implementation, from implementation to post-implementation, as well as the evaluation of long-term sustainability (>6-months post-implementation). SQL Server queries will be utilized to automatically update the data reported in the study's Microsoft Access database. The Access database front-end will be comprised of a form with buttons for on-demand updates to results from the existing queries (e.g., ISI scores from progress notes). Also, we will closely monitor the ongoing electronic health record update to Cerner. While the Cerner integration is not expected to impact this study, if participating sites do integrate Cerner during the study period, we will adapt our automated data query methods or utilize a standardized chart review form to collect data from individual Veteran records.

Reach, the primary outcome, will calculate the number of Veterans in PCMH who receive insomnia-related care. This may include (1) Veterans in Primary Care/PCMH clinics who receive an insomnia diagnostic code and/or a sedative hypnotic medication (see Table 4); (2) Veterans in Primary Care/PCMH clinics who initiate BBTI or CBT-I (indicated by a relevant progress note/encounter); (3) the proportion of Veterans in Primary Care/PCMH clinics who initiate BBTI/CBT-I relative to the Veterans in Primary Care/PCMH clinics who are eligible to initiate BBTI/CBT-I. Data collection will begin 1/1/2020 in order to compare to data during the study period (beginning 1/1/2021) and evaluate change. While the focus is on BBTI, initiation and engagement in CBT-I is also relevant as it will be important to evaluate different insomnia services delivered in Primary Care/PCMH (e.g., diagnoses, medications, BBTI, CBT-I).

Tracking these insomnia-related variables will allow us to measure trends in treatment initiation, diagnosis, and prescribing practices at different stages of the study (and prior to the study). However, this will still likely represent an underestimate of potential Reach since there will be Veterans with insomnia who turn down a PCMH visit, do not receive an insomnia diagnosis, and decline a sedative-hypnotic.

Table 4. Insomnia diagnoses and prescription sedative-hypnotics eligible for Reach denominator.

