## 5.6 Data Analysis

Specific Aim 1: To test the impact of BBTI+IS to improve RE-AIM outcomes and the sustainable delivery of BBTI without implementation support.

**Analyses.** Power estimates were based on Reach and were conducted for an incomplete stepped-wedge design with four steps (four participating sites) with site randomization every six months. An incomplete design was used since the implementation phase stops after 12-months rather than continuing until study completion. Using VA 2018 data from Primary Care and PCMHI dashboards as estimates, all Primary Care patients at the four sites, n=99,572, are considered the potential sample (denominator). The pre-implementation phase sample are Veterans seen for same-day PCMHI care across the four sites, n=4,778 (numerator). Considering the prevalence of insomnia is estimated as 44% of Primary Care patients, n=43,812, and there is minimal insomnia care being conducted in PCMHI currently, we expect to increase overall PCMHI care even if only a fraction of Veterans with insomnia can be reached through the implementation intervention (BBTI+IS). If 0.75% of the estimated 44% with insomnia are seen in PCMHI (n=329, n≈82/site, 1-2 new Veterans per week/site) we have 90% power to detect a significant increase of 6.88% in PCMHI care (4,778 to 5,107) from pre- to implementation phase. See Table 5 for power estimates at different levels of Reach.

Table 5. Power estimates for Reach.

|                          | % of unique Primary Care patients with insomnia (n=43,812) |        |        |        |        |        |          |
|--------------------------|------------------------------------------------------------|--------|--------|--------|--------|--------|----------|
|                          | 2%                                                         | 1.5%   | 1.25%  | 1%     | 0.75%  | 0.5%   | Baseline |
| New PCMHI patients       | 876                                                        | 657    | 548    | 438    | 329    | 219    | --       |
| Current same-day access  | 5,654                                                      | 5,435  | 5,326  | 5,216  | 5,107  | 4,997  | 4,778    |
| Current PC patients      | 99,572                                                     | 99,572 | 99,572 | 99,572 | 99,572 | 99,572 | 99,572   |

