| Same day/PC patients (%) | 5.69                                                       | 5.46   | 5.35   | 5.24   | 5.13   | 5.02   | 4.80     |
| Power (%)                | 100                                                        | 100    | 99.96  | 99.02  | 90.03  | 59.25  | --       |

Descriptive statistics will be used to characterize the participating sites, PCMHI clinicians who are trained in BBTI (enrolled and not enrolled), and Veterans who received insomnia-related care in Primary Care/PCMHI (e.g., BBTI, CBT-I). Key enrolled clinician variables (self-report) will include socio-demographics, training, and work experience (e.g., degree, prior insomnia experience, duration working in PCMHI). For Veterans, variables of interest, from CPRS/CDW, include socio-demographics, vitals, service connection, combat history, and medical and psychiatric disorders, prescription medications, healthcare utilization, and information from progress notes (e.g., ISI scores). For Reach, Adoption, Implementation, and Maintenance outcomes, generalized linear mixed models will be used to compare the impact of the implementation strategy bundle across the three study phases for each site. These models will include a fixed main effect for study phase (pre, implementation, post) and random effects for clinician (nesting of Veterans within clinicians) and site (nesting of Veterans and clinicians within site); the primary comparison will be pre-implementation vs. implementation, with the secondary comparison implementation vs. post-implementation and long-term sustainability. Also, a we will conduct a comparison of outcomes from the study phases vs. a historical period prior to the study (1/1/20 – 12/31/20). While we did not power the study to assess interactions, to the extent possible, a fixed effect for site and the interaction between site and phase, will be introduced to assess differences between sites at the same study phase and differences between sites for the primary and secondary comparisons (e.g., differences from pre-implementation to implementation and from implementation to post-implementation, site 2 vs. site 3).

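### The primary Reach model has a phase effect but no calendar-period effect, so any trend common to all sites biases the pre-implementation vs implementation contrast

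*Combined protocol and SAP*

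**What the plan says.** Section 5.6 (Specific Aim 1) specifies generalized linear mixed models for Reach: "These models will include a fixed main effect for study phase (pre, implementation, post) and random effects for clinician" and site. The primary comparison is pre-implementation vs implementation. Also listed are "the secondary comparison implementation vs. post-implementation and long-term sustainability", a separate "comparison of outcomes from the study phases vs. a historical period prior to the study" (calendar 2020), and, to the extent possible, site and site-by-phase terms. Power was "conducted for an incomplete stepped-wedge design with four steps (four participating sites) with site randomization every six months".

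On timing, the site overview under Consultant says "Training in BBTI will occur at approximately the same time for all sites, the third month of the study". Section 5.1 says "site 1 (randomly selected) will have immediate access to, and support for, the bundle of implementation strategies for 12-months" and "Sites 2, 3, and 4 will enter the pre-implementation monitoring phase for 6-, 12-, and 18-months, respectively", each followed by 12 months of implementation in random order. Data collection runs to month 39.

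No calendar-period term for Reach appears elsewhere. The time effect in section 5.6 belongs to the Effectiveness model and runs from evaluation to last treatment session. Section 5.5 says "Tracking these insomnia-related variables will allow us to measure trends in treatment initiation, diagnosis, and prescribing practices" but ties those trends to no model.

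**The concern.** In a stepped wedge, later calendar time goes with more exposure to the intervention. Randomising the order of the sites allows the two to be separated, but only if the model contains calendar time. With phase alone, the estimate mixes the bundle effect with whatever else changed between earlier and later months. Site effects do not help, because the ordering holds within sites. The 2020 comparison does not help either: it precedes BBTI training and is not part of the primary contrast.

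The documents name possible sources of a common trend without sizing them. The most direct is simultaneous training: uptake or fade afterwards runs along calendar time at every site. CBT-I training continues each year (section 2.1), and CBT-I starts can count toward Reach (section 5.5). Awareness of insomnia is said to be rising (section 3.1). Interview guide 1 (section 10.5) asks about change during COVID.

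At stake is the primary conclusion: the test could be significant with no bundle effect, or could miss a real one.

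**Working it through.** **1. The plan's own power figure.** Section 5.6 gives 90.03% for 4,778 to 5,107 of 99,572. A plain two-sided 5% comparison of two proportions with 99,572 per phase gives 92.4% (62.2% against the stated 59.25% in the 0.5% column), so it does not quite reproduce Table 5. Alpha, ICC, cell sizes and the model behind Table 5 are not stated. Its implied standard error, difference / (1.96 + z of power), is 0.100 to 0.104 percentage points across the four columns from 0.5% to 1.25%.

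**2. Layout.** Section 5.1 gives six six-month periods from month 3 to month 39 (P = pre, I = implementation, M = post).

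| Site | 1 | 2 | 3 | 4 | 5 | 6 |
|---|---|---|---|---|---|---|
| 1 | I | I | M | M | M | M |
| 2 | P | I | I | M | M | M |
| 3 | P | P | I | I | M | M |
| 4 | P | P | P | I | I | M |

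From period 4 on no site is in P, so 3 of the 8 I cells (site 3 in period 4, site 4 in periods 4 and 5) have no concurrent comparison.

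**3. Trend absorbed, by hand (equal cells, no between-site variance).**
- Mean period of P cells: (1 + 1+2 + 1+2+3)/6 = 1.67. Mean period of I cells: (1+2 + 2+3 + 3+4 + 4+5)/8 = 3.00. The gap is 1.33 periods, or 0.667 year.
- A common step absorbs the share of I cells after it minus the share of P cells after it. At 6 months: 7/8 − 3/6 = 0.375. At 12: 5/8 − 1/6 = 0.458. At 18: 3/8 − 0 = 0.375. At 24: 1/8 − 0 = 0.125.

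**4. Trend absorbed, by generalized least squares.** For cell means with design X, covariance V and common trend f, the bias is the implementation element of (X'V⁻¹X)⁻¹X'V⁻¹f. With fixed site effects the linear figure is 0.964 year, and the four steps give 0.464, 0.607, 0.536 and 0.250. Treating long-term follow-up as a fourth phase level raises the linear figure to at most 1.02 years. Adding five period indicators makes every one of these zero.

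**5. Illustration on the power-calculation proxy.** Baseline p = 4,778/99,572 = 4.80%; target 329/99,572 = 0.330 points. Assumed: two-sided 5%, four equal sites, n = 12,447 to 24,893 per site per six months (99,572/8 to 99,572/4), between-site SD 0 to 1 point.
- Common rise equal to the whole target: 6.88%/0.964 = 7.1% to 6.88%/0.667 = 10.3% per year.
- With a 3% yearly fall, a true target effect appears at 1 − 3 × 0.964/6.88 = 58% to 1 − 3 × 0.667/6.88 = 71% of its size.
- Worked case (SD 0, n = 12,447): SE = √[p(1−p)/n × (1/8 + 1/6)] = 0.1035 points. At 3% per year the bias is 0.03 × 4.80 × 0.667 = 0.096 points, or 0.93 SE. The false-positive rate is Φ(0.93 − 1.96) + Φ(−0.93 − 1.96) = 15.3%. Power without a trend is Φ(0.330/0.1035 − 1.96) = 89%.

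Ranges below run over n. Site-by-period variation, where present, is (0.05p)² added to each cell variance.

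| Site SD; site-by-period variation | False positives, 3%/year | False positives, 5%/year | Power, phase only | Power, with period |
|---|---|---|---|---|
| 0; none | 15.3–25.9% | 34.0–59.0% | 89–99% | 77–97% |
| 1 point; none | 24.7–43.9% | 56.6–85.3% | 86–99% | 55–84% |
| 0; 5% | 8.9–9.9% | 16.2–18.9% | 51–60% | 39–47% |
| 1 point; 5% | 12.5–14.3% | 26.2–31.4% | 48–56% | 26–31% |

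False-positive columns are for the phase-only model; with period effects the rate stays at 5% in this calculation. With long-term follow-up as a fourth phase level, period-adjusted power at SD 1 point is 45–73% (no variation) or 21–25% (5%).

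**6. Does Table 5 reveal its model?** With no site-by-period variation, the standard error is 0.073–0.109 points (phase only) and 0.086–0.158 (with period). The implied 0.100–0.104 lies inside both, so Table 5 cannot be assigned to either. With 5% variation both models exceed 0.148.

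**The case against.** The omission itself is hard to dispute, so the best defence concerns its importance.

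- **The trend is hypothetical and most of its sources are weak.** CBT-I is delivered mainly in specialty settings, while Reach counts Primary Care/PCMHI. The COVID question contrasts periods that largely precede the analysed months. The awareness remark is background. This stands in part: only simultaneous training bears directly on months 3 to 39. But the primary test is valid only if there is no common trend over 36 months, which the plan neither states nor defends.
- **The stagger gives some protection.** Five of the eight implementation cells have a concurrent pre-implementation site, and a step at 24 months is absorbed only to 12.5–25%. This stands: the stagger reduces the bias but does not remove it.
- **The figures are not from the planned model.** They use linear cell means with equal variances and no clinician effect, on same-day care rather than a section 5.5 Reach definition. The 85% extreme needs the larger cells, a 1-point site SD and no site-by-period variation. This stands for the percentages, which do not carry over to BBTI/CBT-I starts. The direction of the problem follows from the schedule.
- **The remedy costs power.** This stands, and more so after a small-sample correction. With 3 denominator degrees of freedom (an assumption for four sites), period-adjusted power with three phase levels would be about 31–72% without site-by-period variation and 15–26% with 5%.

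**Conclusion.** The concern holds. As written, the primary Reach contrast is biased by any trend common to the four sites, in either direction. It absorbs 0.67 to 0.96 year of a linear trend and 38 to 61% of a step 6, 12 or 18 months after training, less for a later step. These shares depend on the section 5.1 schedule, an additive scale, equal cell variances and three phase levels. They do not depend on alpha or the choice of Reach measure; cell size matters only slightly, through the weight given to between-site variance.

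Whether a trend will occur, and how large, cannot be known from the documents. The false-positive and power percentages are illustrations under the stated assumptions. The conclusion rests on the design argument: a significant result could not be attributed to the bundle, nor a null result held against it. The stated 90.03% is not shown to be wrong. This should be settled before the primary analysis.

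**What to change.** In section 5.6:

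1. Add fixed calendar-period effects, in six-month steps or finer, to the Reach model.
2. Make the implementation vs pre-implementation coefficient, conditional on period, the primary test, with a small-sample correction suited to four sites (Kenward-Roger, for example).
3. Recompute Table 5 for that model, stating alpha and sidedness, ICC, any site-by-period variation, cell sizes, and whether long-term follow-up is its own phase level.
4. Keep the 2020 data as a separate pre-training comparison, not as site 1's pre-implementation baseline.

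The contrast remains estimable with period effects in this layout. The change needs new wording and a rerun of Table 5, with no new sites, patients or data. The real cost is power. If the recomputed figure is low, the plan should say so and put the weight on the estimate and its confidence interval.

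### The Reach model has no variance term for sites moving between periods, and the plan states no small-sample inference for four randomised sites; modest within-site fluctuation would make the primary test anti-conservative.

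*Combined protocol and SAP*

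**What the plan says.** Section 5.6 (Specific Aim 1, Analyses) plans generalized linear mixed models for Reach. "These models will include a fixed main effect for study phase (pre, implementation, post"), together with "random effects for clinician (nesting of Veterans within clinicians) and site (nesting of Veterans and clinicians within site"). For inference, "the primary comparison will be pre-implementation vs. implementation". To the extent possible, "a fixed effect for site and the interaction between site and phase, will be introduced", to describe differences between sites.

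The power paragraph describes an "incomplete stepped-wedge design with four steps (four participating sites) with site randomization every six months". Section 5.1 sets the schedule: "site 1 (randomly selected) will have immediate access to, and support for, the bundle of implementation strategies for 12-months", while "Sites 2, 3, and 4 will enter the pre-implementation monitoring phase for 6-, 12-, and 18-months, respectively". Data collection continues after that: "for sites 1-3 we will continue to collect data to evaluate long-term sustainability through study month 39".

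The plan does not state a site-by-period or clinician-by-period random effect, an overdispersion term, an intracluster correlation, small-sample degrees of freedom, a permutation test, or alpha and sidedness. It also leaves open the distribution, the unit of analysis and the form of the test for Reach.

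**The concern.** The bundle is switched on and off for a whole site at a time, so the phase contrast compares site-periods. Anything that moves a whole site's rate in one half-year (staffing, clinic access, local policy) adds error shared by every Veteran in that site-period. A site intercept removes only a site's constant level. A clinician intercept removes only constant differences between clinicians. If the shared error is left out, the standard error reflects Veterans counted as independent within site and clinician, and it stays small however much sites move.

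At stake are the p-value and confidence interval for the primary comparison. The target effect is a relative increase of 6.88%. Table 1 lists 9 to 19 clinicians per site, so one clinician is about 5% (1/19) to 11% (1/9) of a site's staff, which is the same order as the target.

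**Working it through.** **Inputs.** From section 5.6: 99,572 Primary Care patients, 4,778 seen same-day at baseline (p = 4.80%), 5,107 at the target, stated power 90.03%. From section 5.1: months 3 to 39 make six half-years, so 4 x 6 = 24 site-periods. With B pre-implementation, I implementation, P post and L long-term, the four sequences are IIPLLL, BIIPLL, BBIIPL and BBBIIP. Site 1 has no pre-implementation half-year, so the within-site contrast rests on three sites. Assumed: two-sided alpha of 0.05, equal sites (99,572/4 = 24,893), independent site-period noise with CV c, and a Wald z test.

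**1. The plan's own power.** A Poisson comparison of the two totals gives 329/√(4,778 + 5,107) − 1.96 = 1.35, or 91.1%. For the 0.5% column it gives 60.1%, against 59.25% stated. Two independent proportions give 92.4% and 62.2%. The exact formula cannot be identified, but Table 5 implies a variance only 1.07-1.11 times that of independent Veterans.

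**2. False-positive rate of the stated model.** The sampling CV of one site-period rate is s = √((1 − p)/(n·p)). This is 2.8% at n = 24,893 and 4.0% at n = 12,446; the smaller n applies if only half the annual patients are seen per half-year. Extra noise multiplies the true variance of the phase contrast by 1 + c²/s², while the model's own variance ignores it. So

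size = 2·[1 − Φ(1.96/√(1 + c²/s²))].

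Example at n = 24,893 and c = 5%: 1 + 0.05²/0.02823² = 4.14, and 1.96/√4.14 = 0.96, so size = 33.5%.

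| CV c | n = 24,893 | n = 12,446 |
|---|---|---|
| 0% | 5% | 5% |
| 1% | 6.5% | 5.7% |
| 2% | 11% | 8% |
| 3% | 18% | 12% |
| 5% | 34% | 22% |
| 10% | 59% | 47% |

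Simulation of the random-intercept model at n = 24,893 agrees: 5%, 11.5%, 35.5% and 59% at CV 0, 2, 5 and 10%. Size passes 10% at a CV of about 1.8% (n = 24,893) or 2.6% (n = 12,446).

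**3. Do period fixed effects cure it?** No. The factor 1 + c²/s² applies to every contrast of site-period rates, whatever fixed effects are fitted. Simulated size with period effects was 12%, 33% and 60% at CV 2, 5 and 10% (n = 24,893).

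**4. A small-count Reach measure.** If the 82 new Veterans per site are a 12-month count, there are about 41 per site per half-year, so s² = 1/41. At c = 5%, 1 + 0.05²·41 = 1.10 and size is 6%. At c = 10% the factor is 1.41 and size is 10%; at c = 20% it is 2.64 and size is 23%.

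**5. Power with the variance included.** Analyse the log rate per site-period. The phase contrast has variance v·(s² + c²), where v comes from the design matrix. Site (4 parameters) plus three phases (2 more) leaves 24 − 6 = 18 df, with v = 0.321. Adding period (5 more) and a long-term phase (1 more) leaves 12 df, with v = 0.910. The target is ln(5,107/4,778) = 0.0666. At c = 5% and n = 24,893 the standard error is √(0.321 × 0.00330) = 0.0325 in the first case and 0.0548 in the second.

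| CV c | Site + phase, 18 df | Plus period and fourth phase, 12 df |
|---|---|---|
| 0% | 97-98% | 60-62% |
| 2% | about 90% | 46-49% |
| 3% | 75-77% | about 34% |
| 5% | 47-51% | 19-20% |
| 10% | 18-20% | 8-10% |

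Ranges span this calculation and the simulations. Simulated false positives were 4.4-5.3% for the 18-df analysis at every CV tried. Analyses with 12 df also held close to 5%.

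**The case against.** Five points can fairly be made for the plan.

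- **No figure for the variation.** A reader might infer that normal half-year fluctuation is known to push the error far above 5%. The documents contain no within-site variation figure of any kind. At CV 1% the size is only about 6%. This stands, so the claim has to be conditional.
- **Four sites.** A reader might infer that four sites with large-sample inference inflate the error in themselves. In this setting they do not: with no site-by-period variation the size is about 5%. The cause is the missing variance.
- **Silence on the test.** A Wald test is an assumption here. An overdispersed model of site-period counts is not excluded and would absorb part of the variance. The accurate charge is that the plan does not specify it, and for a primary test that is itself a gap.
- **The measure.** The 4.80% rate is same-day PCMHI care, used for power. It is not one of the Reach measures listed in section 5.5. For treatment-initiation counts the inflation is small up to CV 10%. The large figures belong to the powered rate only. They also shrink if the 2018 totals are annual and each half-year holds about 12,446 patients per site.
- **Site-by-phase terms.** These could make a change confined to one site visible. They do not put the missing variance into the error of the primary comparison.

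**Conclusion.** The point holds in conditional form. As written, the Reach model has no site-by-period variance, and the plan states no small-sample inference. If half-year site rates vary by 2-10% beyond sampling, the nominal 5% test on the powered rate has about 10-60% false positives at 24,893 per site-period and about 7-50% at 12,446. It has about 5% if there is no such variation. These sizes rest on equal sites, independent site-period noise, two-sided 0.05 and a Wald z test.

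Table 5 leaves almost no room for this variance. Its implied excess of at most 1.11 corresponds to a CV of about 2.8% × √0.11 = 0.9%, if all of it were an allowance for site movement.

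A reader might also attribute the whole fall in power, to about 20% at CV 5%, to site-by-period variance. That would be wrong. Calendar period and a fourth phase level already bring power to about 60% at CV 0, and that is a separate modelling decision.

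**What to change.** Before Reach is analysed, amend section 5.6 as follows.

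1. Analyse Reach at site-by-period level, or add a site-by-period random effect or overdispersion term to the mixed model.
2. Test phase with a t reference on the residual site-period degrees of freedom: 18 with site and the three stated phases, 12 if calendar period and a separate long-term phase are also included. State alpha and sidedness.
3. Report a permutation test over the 4! = 24 site orders as a sensitivity check. Its smallest possible p-value is 1/24 = 0.042, so it is too coarse to be the main test.
4. Restate Table 5 under this analysis for a stated CV range and for the Reach measure that will be primary. Show the loss from period effects and the fourth phase level separately. Reach data from 1/1/2020 onward, which section 5.5 already plans to collect, could inform the CV.

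The cost is SAP wording and a little programming, with wider intervals and a less favourable stated power. No extra sites or data are needed.
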